8.4 Study Records

The following documents will be considered study records:

- Consent forms
- Case report forms
- Subjects' medical records

- Protocol
- Regulatory documents

Study records will be securely stored in the PI's office for internal use during the study. The PI is responsible for maintaining the study documentation. All study research members will have access to study records. At the end of the study, all records will continue to be kept in a secure location for as long a period as dictated by the reviewing IRB, Institutional policies, regulatory, or sponsor/funding agency requirements.

The study records will not include the participant's contact or identifying information. Rather, individual participants and their research data will be identified by a unique study identification number. The study data entry and study management systems used will be secured and password protected. At the end of the study, all study databases will be de-identified and archived on the server used by the PI's lab.

8.5 Access to Source

Source data include all information and original records of clinical findings, observations, or other activities necessary for the reconstruction and evaluation of the trial.

Source documentation include:

- Study records
- Electronic medical records
- Laboratory reports
- Memoranda
- Subject diaries
- Subject questionnaires
- Recorded data from automated instruments.

Source documents should be neat and legible. When making changes or corrections, the original entry should be crossed out with a single line, initialed and dated.

Hardcopies of the study visit worksheets will be provided for use as source document worksheets for recording data for each participant enrolled in the study. Data recorded in the electronic case report form (eCRF) derived from source documents should be consistent with the data recorded on the source documents.

Clinical data (including adverse events (AEs), concomitant medications, and expected adverse reactions data) will be entered into an online database as described above.

The investigational site will provide direct access to all trial related sites, source data/documents, and reports for the purpose of monitoring and auditing by the sponsor, and inspection by local and regulatory authorities.

8.6 Retention of Records

Study documents will be retained for a minimum of 2 years after the completion of the study. These records will be securely stored and accessible to authorized individuals, such as study personnel and regulatory agencies, when needed.

8.7 Data and Safety Monitoring Plan

We do not anticipate any adverse events. The principal investigator (PI) will monitor the data, assure protocol compliance, and conduct the safety reviews at least annually. The PI evaluates whether the study should continue unchanged, require modifications, or close to enrollment. Any Reportable Events (which are events that are serious or life-threatening and unanticipated (or anticipated but occurring with a greater frequency than expected) and possibly, probably, or definitely related) Unanticipated Problems Involving Risks to Subjects or Others (UPIRSO) will be reported to the IRB and any appropriate funding and regulatory agencies. Unanticipated Problems Involving Risks to Subjects or Others that may require a temporary or permanent interruption of study activities (if possible) will be reported, followed by a written report within 5 calendar days of my becoming aware of the event to the IRB and any appropriate funding and regulatory agencies. The PI will apprise fellow investigators and study personnel of all UPIRSOs and adverse events that occur during the conduct of this research project. The PI will report all UPIRSOs and adverse events that occur during the conduct of this research project to other applicable oversight bodies as required within applicable reporting timeframes.

9 Study Considerations

9.1 Institutional Review Board (IRB) Review

The protocol will be submitted to the IRB for review and approval. Approval of the protocol must be obtained before initiating any research activity. Any change to the protocol will require an approved IRB amendment before implementation. The IRB will have final determination whether informed consent and HIPAA authorization are required.

Study closure will be submitted to the IRB after all research activities have been completed.

Other study events (e.g. data breaches, protocol deviations) will be submitted per Yale policies.

9.2 Research Personnel Training

The training will cover all aspects of the study design, protocol, and procedures, including ethical considerations, informed consent and data collection. The training will be documented and kept on file for future reference and potential audits.

The training process will cover the following key areas:

- Study objectives and hypotheses - The research assistants will have a clear understanding of the overall aim and specific hypotheses of the study.

- Study protocol and procedures - The research assistants will be familiar with the study protocol and procedures, including patient enrolment, data collection, and adverse event reporting.
- Data collection instruments - The research assistants will be trained on the use of the study's data collection instruments, including the clinician-rated and patient-rated outcome questionnaires and the custom side effect questionnaire.
- Patient interaction - The research assistants will be trained on how to interact with patients during the study, including how to approach patients for participation, explain the study's aims and procedures, and handle any questions or concerns that may arise.
- Confidentiality and ethics - The research assistants will be trained on the importance of maintaining patient confidentiality and adhering to ethical standards in research.
- Data management and analysis - The research assistants will be familiar with the data management including data coding, data entry, data monitoring, and handling of missing data.

The training process will also include a hands-on component, such as role-playing or mock data collection, and then doing real data collection with supervision for the first two times to help the research assistants gain practical experience and ensure they are confident in their role.

9.3 Study Monitoring

Study monitoring is conducted to ensure that the rights and well-being of trial participants are protected, that the reported trial data are accurate, complete, and verifiable, that the facilities and staffing are adequate for continued study conduct, and that the conduct of the trial is in compliance with the currently approved protocol/amendment(s), with International Council for Harmonization Good Clinical Practice (ICH GCP), and with applicable regulatory requirement(s) including federal, state and local regulations and institutional policies and procedures. In addition to all applicable regulatory bodies, the Yale Center for Clinical Investigation (YCCI), as the sponsor of the study, will oversee the study.

9.4 Unanticipated Problems and Protocol Deviations

A protocol deviation is any noncompliance with the protocol. The noncompliance may be either on the part of the participant, the investigator, or the study staff. As a result of deviations, corrective actions are to be developed by the site and implemented promptly.

It is the responsibility of the investigator to identify and report deviations within five working days of identification of the protocol deviation. All deviations must be addressed in study source documents, reported to the study sponsor, and the reviewing Institutional Review Board (IRB) per their policies.

Unanticipated problems involving risks to participants or others include, in general, any incident, experience, or outcome that meets all of the following criteria:

- Unexpected in terms of nature, severity, or frequency given (a) the research procedures that are described in the protocol-related documents, such as the Institutional Review Board (IRB)-approved research protocol and informed consent document; and (b) the characteristics of the participant population being studied;
- Related or possibly related to participation in the research ("possibly related" means there is a reasonable possibility that the incident, experience, or outcome may have been caused by the procedures involved in the research); and
- Suggests that the research places participants or others at a greater risk of harm (including physical, psychological, economic, or social harm) than was previously known or recognized.

If the study team becomes aware of an unanticipated problem (e.g. data breach, protocol deviation), the event will be reported to the IRB by email.

The UP report will include the following information:

Protocol identifying information: protocol title and number, PI's name, and the IRB project number;

- A detailed description of the event, incident, experience, or outcome;
- An explanation of the basis for determining that the event, incident, experience, or outcome represents an UP;
- A description of any changes to the protocol or other corrective actions that have been taken or are proposed in response to the UP.

To satisfy the requirement for prompt reporting, UPs will be reported using the following timeline:

- UPs will be reported to the IRB within five of the investigator becoming aware of the event.

9.5 Study Discontinuation

The study might be discontinued in several circumstances, including if there are any adverse events or safety concerns that put the participants at risk, if the enrollment rate is significantly lower than expected and impacts the validity of the results, or if there are changes in regulations or ethical guidelines that make it necessary to discontinue the study. Additionally, the principal investigator may choose to discontinue the study if it is found to be ineffective or if funding for the study is withdrawn. In any of these circumstances, the participants will be informed and appropriate measures will be taken to ensure their safety and wellbeing.

9.6 Study Completion

This study is expected to continue for two years. The expected completion date is 5/2025. IRB and the sponsored will be notified if the completion date of the study is expected to change, as applicable.

9.7 Conflict of Interest Management Plan

The independence of this study from any actual or perceived influence, such as by the pharmaceutical industry, is critical. Therefore, any actual conflict of interest of persons who have a role in the design, conduct, analysis, publication, or any aspect of this trial will be disclosed and managed. Furthermore, persons who have a perceived conflict of interest will be required to have such conflicts managed in a way that is appropriate to their participation in the trial. The study leadership in conjunction with the appropriate conflict of interest review committee has established policies and procedures for all study group members to disclose all conflicts of interest and will establish a mechanism for the management of all reported dualities of interest.

All investigators will follow the applicable conflict of interest policies.

9.8 Funding Source

The study is funded by YCCI by a UL1 Clinical Junior Faculty Pilot Award.

9.9 Publication Plan

This study will be conducted in accordance with the following publication and data sharing policies and regulations: National Institutes of Health (NIH) Public Access Policy, which ensures that the public has access to the published results of NIH funded research. It requires scientists to submit final peer-reviewed journal manuscripts that arise from NIH funds to the digital archive PubMed Central upon acceptance for publication.

This study will comply with the NIH Data Sharing Policy and Policy on the Dissemination of NIH-Funded Clinical Trial Information and the Clinical Trials Registration and Results Information Submission rule. As such, this trial will be registered at ClinicalTrials.gov, and results information from this trial will be submitted to ClinicalTrials.gov. In addition, every attempt will be made to publish results in peer-reviewed journals.

10 Appendices

Appendix #	Title	Section	Topic
Appendix 1	Feedback form	4	Study design
Appendix 2	Adverse events form	4	Study design

Appendix 1 – Presentation Feedback Form

With regards to the presentation you just received, please answer the following questions:

- The overall information provided was informative

Fully disagree Fully agree
 0 1 2 3 4 5 6 7 8 9 10

- The slides were helpful

Fully disagree Fully agree
 0 1 2 3 4 5 6 7 8 9 10

- The presenter was able to relay the information effectively

Fully disagree Fully agree
 0 1 2 3 4 5 6 7 8 9 10

- My questions were satisfactorily addressed either during the presentation or afterwards by the presenter

Fully disagree Fully agree
 0 1 2 3 4 5 6 7 8 9 10

- I wish I could receive a similar presentation for any treatments I receive in the future (psychiatric or non-psychiatric)

Fully disagree Fully agree
 0 1 2 3 4 5 6 7 8 9 10

Appendix 2- Side Effects Questionnaire

Please ask each of the items below from the participant. Provide explanation for items as appropriate (e.g., for tachycardia you can mention “heart racing” or “rapid heartbeat”)

Tachycardia

None Mild Moderate Severe

Vertigo

None Mild Moderate Severe

Nausea

None Mild Moderate Severe

Vomiting

None Mild Moderate Severe

Diarrhea

None Mild Moderate Severe

Dry Mouth

None Mild Moderate Severe

Constipation

None Mild Moderate Severe

Feeling drunk

None Mild Moderate Severe

Feeling abnormal

None Mild Moderate Severe

Increased blood pressure

None Mild Moderate Severe

Dizziness

None Mild Moderate Severe

Sedation

None Mild Moderate Severe

Headache

None Mild Moderate Severe

Dysgeusia

None Mild Moderate Severe

Hypoesthesia

 None	 Mild	 Moderate	 Severe
-------------------------------	-------------------------------	-----------------------------------	---------------------------------

Lethargy

 None	 Mild	 Moderate	 Severe
-------------------------------	-------------------------------	-----------------------------------	---------------------------------

Dysarthria

 None	 Mild	 Moderate	 Severe
-------------------------------	-------------------------------	-----------------------------------	---------------------------------

Tremor

 None	 Mild	 Moderate	 Severe
-------------------------------	-------------------------------	-----------------------------------	---------------------------------

Mental impairment

 None	 Mild	 Moderate	 Severe
-------------------------------	-------------------------------	-----------------------------------	---------------------------------

Dissociation

 None	 Mild	 Moderate	 Severe
-------------------------------	-------------------------------	-----------------------------------	---------------------------------

Anxiety

 None	 Mild	 Moderate	 Severe
-------------------------------	-------------------------------	-----------------------------------	---------------------------------

Insomnia

 None	 Mild	 Moderate	 Severe
-------------------------------	-------------------------------	-----------------------------------	---------------------------------

Euphoric mood

 None	 Mild	 Moderate	 Severe
-------------------------------	-------------------------------	-----------------------------------	---------------------------------

Pollakiuria

 None	 Mild	 Moderate	 Severe
-------------------------------	-------------------------------	-----------------------------------	---------------------------------

Nasal discomfort

 None	 Mild	 Moderate	 Severe
-------------------------------	-------------------------------	-----------------------------------	---------------------------------

Throat irritation

 None	 Mild	 Moderate	 Severe
-------------------------------	-------------------------------	-----------------------------------	---------------------------------

Oropharyngeal pain

 None	 Mild	 Moderate	 Severe
-------------------------------	-------------------------------	-----------------------------------	---------------------------------

Hyperhidrosis

 None	 Mild	 Moderate	 Severe
-------------------------------	-------------------------------	-----------------------------------	---------------------------------

11 List of Tables

1 Table 1: Visit Schedule Table

12 References

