Patients who are deemed clinically appropriate for esketamine will be approached for participation in the study. The eligible and consented participants will be randomized at a 1:1 ratio into “intervention” and TAU groups, with the intervention group being presented with the presentation prior to the first treatment, and to receive a “follow up” session within 24 hours after the first treatment. Both groups will otherwise receive treatment as usual during the course. Assessments including treatment expectations and depression severity will be done at baseline, within 24 hours after treatments 1, 2 and 8.

Study Duration

2 years

Outcome Variables

Primary outcome: Group difference in change in question 6 of the CEQ-6 from baseline to after the presentation

Secondary Outcome: Group difference in change in MADRS score from baseline to 24 hours after first treatment

Exploratory outcomes:

Group difference in change in CEQ-6 from baseline to 24 hours after first treatment and after follow-up session

Group difference in change in MADRS score by the end of the acute series of treatments

Group difference in the side effect profile

Locations/Facilities

Yale Psychiatry hospital (YPH) Interventional Psychiatry Services (IPS) unit

Abbreviations

Abbreviation	Explanation
AE	Adverse Events
CMP	Clinical monitoring plan
CEQ-6	Credibility and Expectancy Scale
CRF	Case report form
DCC	Data coordination center
DHHS	Department of Health and Human Services
DSMB	Data Safety Monitoring Board
DRE	Department of Health and Human Services
EC	Ethics Committee
eCRF	Electronic Case Report Forms
GCP	Good clinical practice
HIPAA	Health Insurance Portability and Accountability Act
MADRS	Montgomery-Asberg Depression Rating Scale
NCT	National Clinical Trial
NIH	National Institutes of Health
PI	Principal Investigator

QA	Quality Assurance
QC	Quality Control
QIDS-SR	Quick Inventory of Depressive Symptomatology
SAE	Serious Adverse Event
SAP	Statistical Analysis Plan
SMC	Safety Monitoring Committee
SOP	Standard Operating Procedure
TAU	Treatment as usual
UP	Unanticipated Problem
YCCI	Yale center for clinical investigation

Glossary of Terms

Glossary	Explanation
Adverse Event	Any event associated with esketamine treatment or the virtual presentation and follow-up sessions whether or not considered therapy related.
Dysgeusia	Altered taste

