3.2 Hypothesis

Hypothesis 1: A positive presentation highlighting the rapid onset effects and positive therapeutic outcomes observed in prior clinical trials and clinical care will increase the expectation of improvement from esketamine treatment compared to the treatment-as usual (TAU) group.

Hypothesis 2: A post-treatment “debriefing” session after first the treatment to provide encouragement and reassurance, will further consolidate the expectation of improvement from esketamine treatment.

Hypothesis 3: A positive presentation highlighting the rapid onset effects and positive therapeutic outcomes observed in prior clinical trials and clinical care combined with a post-treatment “debriefing” session after first the treatment to provide encouragement and reassurance will enhance treatment response compared to the TAU group.

Hypothesis 4: Highlighting a specific side effect during the presentation will result in a difference on the side effect profile of the treatment.

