The intervention consists of a short presentation provided to the participants within 72 hours prior to the first treatment of the acute course (see study course below). Both groups will receive the information considered necessary for informed consent for esketamine treatment as part of usual clinical care. The presentation will be in addition to this process. The presentation will be factual, however it will emphasize the effectiveness of the treatment, and provide notable encouragement and reassurance. The actual treatments will be provided as usual with no change or alteration in dosing, course or other aspects of the treatment.

The intervention group will additionally receive a follow up session within 24 hours after the first treatment to provide encouragement and reassurance. There are two different versions for the follow up session, with each participant receiving one of the versions depending on whether they have noticed any improvements since the first treatment. The contents of these sessions will remain factual, but with differing emphasis on encouragement and reassurance depending on participants’ experience with the first treatment.

Study course

Participants in the intervention group will receive the presentation within 48 hours before the first treatment of the acute course of esketamine. They will also receive the follow up session within 24 hours after the first treatment, immediately after assessments are completed.

Assessments will be done at baseline, within 24 hours after treatments 1, 2 and 8, as detailed in Table 1. Assessments will be identical for both groups, with the exceptions described below.

Assessments

Intervention group specific assessments:

Participants will provide feedback regarding the presentation using a custom form (Appendix 1) before treatment 1 and at the end of treatment visit.

Assessments received by both groups:

Participants’ expectations will be assessed by Treatment Credibility and Expectancy Scale (CEQ-6).

[figure not shown]
Symptom severity will be assessed by a blinded assessor using a Clinician Rated Outcome questionnaire (MADRS) and a Patient Rated Outcome questionnaire (QIDS-SR16).

[figure not shown]
Side effects will be assessed by a custom questionnaire (Appendix 2) based on the side effects reported on the prescription label for esketamine.

End of treatment debriefing session:

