6.1 Study Procedures

Potential subjects will be referred to the study team by the interventional psychiatry physician who has seen the patient in clinical evaluation for esketamine, after ascertaining their agreement to be approached for the study. At this time, the patient will be reached out by a study team member and informed about the study.

Screening / Intake Visit

It is estimated the screening intake will take approximately 2 hours. It will consist of the following procedures and assessments and can be completed in up to 5 days:

- a. Informed Consent: A delegated study team member will discuss risks and benefits of participation and review the study overview with the patient as explained above. The patient will sign the informed consent form prior to any study procedures being performed.
- b. Clinical and Demographic Intake (including medical and psychiatric history, medication history, and current medications)
- c. Montgomery-Asberg Depression Rating Scale (MADRS) and Quick Inventory of Depressive Symptomatology (QIDS-SR16)
- d. CEQ-6 questionnaire regarding upcoming treatment course with esketamine
- e. Review of Inclusion/Exclusion Criteria by investigator

Presentation Visit (Intervention group only)

The intervention consists of a short virtual (via Zoom or similar technology) presentation provided to the participants, within 72 hours before the first treatment with esketamine. The presentation includes predetermined slides and content (the presenter will cover the same

slides and topics but will avoid a strict script to retain the personalized feeling of the presentation, an aspect believed to be crucial to the non-specific effects. Further, patients are allowed to engage, ask questions etc.) The presentation will remain factual and provide information from peer-reviewed literature. However, it is designed to convey a strong positive message, highlighting the effectiveness of the treatment. Additionally, a mild and temporary known side effect of the treatment (dysgeusia) will be intentionally highlighted to assess the 4th hypothesis.

Treatment visits:

Both groups will receive the usual treatment and care. Immediately before first and second treatments both groups will complete the CEQ-6 questionnaire. Additionally, the intervention group will complete the presentation feedback form prior to the first treatment. The rest of the treatments (i.e. treatments 3 to 8) will be done without any assessments.

Follow-up visit:

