8.2 Data Quality Assurance

Data quality assurance is a crucial aspect of this study to ensure the validity and reliability of the results. A number of steps will be taken to maintain data quality, including the use of standardized and validated assessment tools (CEQ-6, MADRS, QID-SR16, and custom questionnaire), training of the blinded assessor to ensure consistent administration of the assessment tools, regular monitoring of data collection to identify and address any discrepancies, and proper storage and management of the collected data.

We will perform internal quality management of study conduct, data collection, documentation and completion.

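### Appendix 2 leaves the explanation of dysgeusia to the interviewer while only one arm's presentation highlights it, so part of an exploratory Hypothesis 4 difference could reflect understanding of the item

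*Combined protocol and SAP*

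**What the plan says.** Hypothesis 4 (Section 3.2) reads: "Highlighting a specific side effect during the presentation will result in a difference on the side effect profile of the treatment". To test it, Section 6.1 states that "a mild and temporary known side effect of the treatment (dysgeusia) will be intentionally highlighted to assess the 4th hypothesis". That visit is headed "Presentation Visit (Intervention group only"). For TAU, Section 4 (Intervention) says only that "Both groups will receive the information considered necessary for informed consent for esketamine treatment as part of usual clinical care"; how that information describes dysgeusia is not given.

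Side effects are recorded on the Appendix 2 form, 24 hours after the first treatment and at the end-of-study visit (Table 1). Its instruction is "Please ask each of the items below from the participant. Provide explanation for items as appropriate". The one example of lay wording begins "for tachycardia you can mention". Dysgeusia, hypoesthesia, dysarthria, pollakiuria and hyperhidrosis appear as bare terms with a four-level severity scale. The protocol's own glossary explains dysgeusia as "Altered taste", but the form does not carry that wording.

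Section 8.2 bases data quality partly on "the use of standardized and validated assessment tools (CEQ-6, MADRS, QID-SR16, and custom questionnaire"), together with assessor training for consistent administration. Section 9.2 includes the side-effect form in staff training, with practice and two supervised collections. The side effect profile is an exploratory outcome (Section 4.2.2).

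**The concern.** The manipulation that tests Hypothesis 4 may also teach one arm what the question means. A patient who has been told about this side effect at length is likely to know what the dysgeusia item asks. A TAU patient with altered taste who does not know the word, and does not have it explained, may answer None. The arms could then differ in reported dysgeusia with the same true rate in both, and the error would run in the hypothesised direction.

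Comprehension of the item is not recorded, so no analysis of the collected data could separate this from a nocebo effect. What is at stake is the interpretation of one exploratory hypothesis. It still matters, because Section 2.2 accepts possible extra dysgeusia in the intervention arm as a risk of the emphasis, and Section 2.1 says the data will support later proposals.

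**Working it through.** **Inputs from the documents.** 17 patients per arm (Sections 5.2 and 7.1); side effects may be coded present or absent (Section 7.4); they are to be compared between arms (Section 7.3). The plan gives no expected dysgeusia rate and names no test for side effects, so there is no planned figure to reproduce.

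**Assumptions.** The true dysgeusia rate p is the same in both arms, at 20% or 40%. Every affected intervention patient recognises the item. A fraction r of affected TAU patients recognises it, either unaided or because it was explained, with r = 0.9, 0.7 or 0.5. None of these values comes from the documents. Fisher's exact test, two-sided at 0.05, is chosen here for illustration.

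**Formulas.** Expected reported rate: p in the intervention arm and p × r in TAU. Spurious difference = p − p × r = p(1 − r). Spurious risk ratio = p / (p × r) = 1/r.

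**Example.** At p = 0.40 and r = 0.7, the reported TAU rate is 0.40 × 0.7 = 0.28. The difference is 0.40 − 0.28 = 0.12, and the risk ratio is 1/0.7 = 1.4. Expected counts are 17 × 0.40 = 6.8 against 17 × 0.28 = 4.8.

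**Results.** The last column sums the two binomial distributions over every 17 v 17 table with Fisher p<0.05.

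| True rate p | TAU recognition r | Reported TAU rate | Spurious difference | Risk ratio | Fisher p<0.05 |
|---|---|---|---|---|---|
| 20% | 1.0 | 20% | 0 points | 1.0 | 1.9% |
| 20% | 0.9 | 18% | 2 points | 1.1 | 2.0% |
| 20% | 0.7 | 14% | 6 points | 1.4 | 3.0% |
| 20% | 0.5 | 10% | 10 points | 2.0 | 5.4% |
| 40% | 1.0 | 40% | 0 points | 1.0 | 2.2% |
| 40% | 0.9 | 36% | 4 points | 1.1 | 2.5% |
| 40% | 0.7 | 28% | 12 points | 1.4 | 5.7% |
| 40% | 0.5 | 20% | 20 points | 2.0 | 14.2% |

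The r = 1.0 rows show the situation that a common explanation aims for: no expected difference, and Fisher p<0.05 in about 2% of trials. At this sample size the artefact is more likely to shift the estimate than to produce a significant result.

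**The case against.** The strongest reply is that the mechanism needs the form's instruction to fail. Staff may explain any item, an obscure word is where explanation is most plainly called for, and patients can ask. Training is promised twice, once naming this form. This stands as a reason why the artefact may be small. It does not remove the gap: explanation is permitted but not required, no common wording is given, and an interviewer could reasonably skip it for a patient who seems to know the term and improvise for one who does not.

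A second reply is that the slides and the consent wording are not in the documents. If the slides use only a lay phrase, the intervention arm gains no vocabulary advantage; if usual consent already conveys the term, TAU has no deficit. This stands in full and is why no size can be fixed.

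Blinding is a weaker defence. Section 6.1.1 names a blinded assessor for symptom severity and does not say who asks about side effects. Blinding would not equalise what patients understand in any case.

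A reader might infer that a positive Hypothesis 4 result would simply be word recognition, or that the arms are known to understand the item differently. The documents support neither; they show only that the procedure does not rule it out. The Section 8.2 description of the custom form as standardized and validated is a separate wording point and is not evidence of bias.

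**Conclusion.** The point holds as a possibility of unknown size. The item on which exploratory Hypothesis 4 turns is printed without a lay gloss, its explanation is discretionary, and only one arm has the effect highlighted beforehand, so part of an observed difference could come from understanding of the item.

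The calculated range depends entirely on the assumed recognition rates, equal true rates and full recognition in the intervention arm. The 20-point figure is the upper end of that range and needs half of affected TAU patients to miss the item despite permitted explanation. The primary outcome (CEQ-6 question 6) and the secondary outcome (MADRS) are untouched. This is an improvement worth considering, not a flaw that threatens the trial.

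**What to change.** Print one fixed lay description on the Appendix 2 form beside dysgeusia, using the glossary's "Altered taste", and beside the other technical terms such as hypoesthesia, dysarthria, pollakiuria and hyperhidrosis. Read it to every participant in both arms at both visits, whether or not they appear to know the term. Further clarification may be given if asked. Everyday items such as headache or nausea need no script.

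If data collection has begun, record which form version each patient answered. In Section 8.2, take the custom questionnaire out of the list of standardized and validated tools.

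The cost is a revised form, an edit to Section 8.2 and an IRB amendment, with possibly two form versions in the data. No new visits, staff or patients are needed. The change closes the vocabulary route only. Heightened attention to taste after the presentation would remain, as it should, because that is part of the effect under study.
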